TITLE: CLINICAL PHARMACOLOGY OF ELECTRONIC CIGARETTES

NCT02470754

[figure not shown]
Date: 4/ 15 / 2019

Abbreviations

EC	Electronic Cigarette
TC	Tobacco Cigarette (Commercially Manufactured or Available)
PK	Pharmacokinetic
CI	Confidence Interval
SD	Standard Deviation
BMI	Body Mass Index
HR	Heart Rate
SBP	Systolic Blood Pressure
DBP	Diastolic Blood Pressure
hr	Hour
AUCinf	Area under the plasma concentration time curve from zero to the last measured time
AUClast	Area under the plasma concentration time curve extrapolated from zero
C_{MAX}	Peak Plasma Concentration
T_{MAX}	Time of Peak Plasma Concentration
T_{Half}	Half-Life
ANOVA	Analysis of Variance
SAS	Statistical Analysis System

Study Design

This is a within-subject two-arm crossover study design evaluating the safety and addictive potential of EC compared to TC

Study Endpoints

On the first hospital day in each treatment arm the subject will use their product at 9 AM in a standardized protocol. EC use will be one puff every puff every 30 seconds for a total of 15 puffs on 1st generation devices and 10 puffs on 2nd/3rd generation devices.

Endpoint (s): Systemic Nicotine Exposure - Baseline Adjusted AUC (Inf), TMAX, CMAX, Half-Life, and PK-Predicted Dose following the standardized puffing protocol. Additional PK Parameters may be calculated as deemed necessary.

Analysis: Linear mixed model

Descriptive Summary Statistics: N, n, arithmetic mean, SD, 95% CI will be used to describe continuous measures including nicotine intake [AUC Inf, AUC Last, PK-predicted dose] related to single use PK. Categorical Data will be described using frequency count and percentage of subjects in each category. Descriptive statistics will be calculated using standard methods.

Statistical Hypothesis

Distributional assumptions underlying the model will be examined by analysis of the residuals and plot of the residuals vs the fitted values.

Treatment effects will be compared by means of repeated measures ANOVA. All significance tests will be two-sided with an alpha level set at 0.05.

Primary Analysis

Crossover analysis was carried out following standard procedures. Following ln-transformation of plasma concentrations treatment effects were compared by means of repeated measures ANOVA. To account for the relatedness in the plasma nicotine measures within each subject during the two treatment periods, a linear mixed model was used to account for non-independence in sequential measurements.

In building the linear mixed-models, baseline-adjusted plasma nicotine concentrations were considered the dependent variable. These models included independent variables of treatment and a dichotomized variable defining order of product assignment. Participant IDs were used as group factor to estimate random effects.

Secondary Analysis

PK data will be presented in graphical and/or tabular form and will be summarized descriptively. Mean Heart Rate, Mean Systolic Blood Pressure and Mean Diastolic Blood Pressure will also be described similarly. Additional toxicant exposure data may be described as necessary.

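### The listed endpoints are per-session PK parameters, but the only model written out has plasma concentrations as response, with its scale unsettled and participant as its only stated grouping factor

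*SAP*

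**What the plan says.** SAP, Study Endpoints, lists "Baseline Adjusted AUC (Inf), TMAX, CMAX, Half-Life, and PK-Predicted Dose" and sets against them "Analysis: Linear mixed model". Each of these is one number per participant per session.

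Statistical Hypothesis names another procedure: "Treatment effects will be compared by means of repeated measures ANOVA".

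Primary Analysis gives two descriptions. The first is "Following ln-transformation of plasma concentrations treatment effects were compared by means of repeated measures ANOVA". The second says that "a linear mixed model was used to account for non-independence in sequential measurements", and then fills in that model. On the response it says that "baseline-adjusted plasma nicotine concentrations were considered the dependent variable". The fixed part is confined to which product was used and the sequence in which the two were assigned. For the random part the SAP says only that "Participant IDs were used as group factor to estimate random effects". Sampling time and a session-within-participant term are not listed, and ln is not mentioned for this response.

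The Abbreviations list defines AUCinf as the area up to the last measured time and AUClast as the extrapolated area, so the two definitions are reversed.

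**The concern.** There are three linked faults.

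- **Response.** An analyst who follows Primary Analysis literally fits no model to AUC(Inf) or CMAX, although Study Endpoints says those are what the mixed model is for.
- **Scale.** The ANOVA sentence takes logs of concentrations; the mixed-model sentence subtracts baseline and mentions no log. The first leads to a ratio of products, the second to a difference in ng/mL. The SAP does not say whether these are one analysis or two, or which one decides.
- **Error structure.** The mixed model is justified by correlation between sequential measurements, but the only grouping stated is participant. Samples from one session share the dose delivered in that session. Treatment varies between sessions, so the session is the unit that sets the precision of the treatment comparison. A participant intercept does not represent it.

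At stake are the interval for the electronic-versus-tobacco cigarette comparison and the two-sided 0.05 level.

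**Working it through.** **No stated figure to reproduce.** The SAP gives no sample size, variance or sampling schedule. The text faults are checked by reading. The size of the error-structure fault is checked under assumptions.

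**Step 1: scale.** Subtracting baseline makes the pre-use value exactly 0, and late values can fall below 0. For example, adjusted values of 0, 8, 6, 4, 2, 0.5 and -0.2 ng/mL (made-up numbers) have logs of minus infinity, 2.08, 1.79, 1.39, 0.69, -0.69 and undefined. Log and baseline correction cannot both apply to every sample without a stated order and a handling rule, and neither is given.

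**Step 2: ANOVA versus mixed model.** With one ln AUC per session, the repeated measures ANOVA F and the squared mixed-model statistic agreed (both 2.715 in a simulated data set). The two method names are not themselves a contradiction.

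**Step 3: error structure by formula.** Assume T samples per session, with a share rho of the within-participant variance lying between sessions. Let a fraction c of the remainder be the common rise and fall over time. For a participant-intercept model with no time term:

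- true variance of the treatment contrast ∝ T·rho + (1−rho)(1−c)
- variance the model assumes ∝ (1−rho)(1−c) + (1−rho)·c·2T/(2T−1) + rho·T/(2T−1)
- type I error ≈ 2[1 − Φ(1.96/√ratio)], where ratio is the first divided by the second

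For rho = 0.1, T = 6, c = 0: 1.500/0.9545 = 1.571, giving 12%. With c = 0.5: 1.050/0.9955 = 1.055, giving 6%. With c = 0.8: 0.780/1.020 = 0.765, giving 2.5%.

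| rho | T | c = 0 | c = 0.5 | c = 0.8 |
|---|---|---|---|---|
| 0.1 | 6 | 12% | 6% | 2.5% |
| 0.1 | 12 | 19% | 13% | 10% |
| 0.3 | 6 | 25% | 21% | 18% |
| 0.3 | 12 | 38% | 36% | 34% |

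The c = 0 column assumes no common time curve, so it gives upper values. The common curve cancels from the treatment contrast but stays in the residual, and so works the other way.

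**Step 4: variance-component simulation under no difference** (4,000 trials per cell; N = 12, 24, 36; T = 6 or 10; session share 0 to 0.5; time-curve variance 0, 1 or 4 times the within-participant variance). The participant-only model rejected in 0.000 to 0.47 of trials. At N = 24, T = 10 and session share 0.3, it rejected in 0.340, 0.157 and 0.020 as the time curve grew. Adding sampling time but no session term gave 0.34 to 0.35 in those three cells. One value per session gave 0.04 to 0.06 in every cell.

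**Step 5: PK simulation under no difference** (2,000 trials per cell; N = 12 to 36; 6 or 12 samples to 240 min; absorption half-life 3 min; elimination half-life 90 to 150 min; boost 6 or 15 ng/mL; median baseline 2 ng/mL; constant or decay-corrected baseline subtraction). The participant-intercept model on baseline-adjusted concentrations rejected in 0.3–23%, 10–50% and 28–61% of trials at within-person delivery ln SD 0.15, 0.3 and 0.5. On ln concentrations, run with decay-corrected subtraction only, it rejected in 7–44% at SD 0.3. A session-level term brought rejection to 3–7%. Per-session ln AUC gave 3–7% and ln CMAX 4–7%.

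**Step 6: AUC labels.** As printed, AUCinf would omit 2^(−240/half-life) of the total if the last sample is at 4 h (an assumption): 16% at a half-life of 90 min and 33% at 150 min.

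**The case against.** The strongest reply is that the SAP never calls the response serial, lists no sampling times, and includes no time covariate. It speaks of relatedness across two treatment periods and of models in the plural, and CMAX is itself a plasma concentration. All of that fits one value per period and one model per endpoint, in which case a participant effect is right. The reference to sequential measurements points the other way, so this reading is possible but not established. Likewise, the plural random effects could include a participant-by-treatment term; in a check of 200 simulated trials (N = 24, 12 samples) that term brought rejection from 45.0% to 7.5%. Either reading clears the error structure. Neither supplies the missing response and scale.

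A reader might infer that the planned test is bound to be too liberal. The document does not support that. With sampling time also left out, the test can be strongly conservative, and the SAP gives neither the schedule nor the variances that would decide.

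A reader might also infer that the conclusion about the products is at risk. At an assumed true ratio of 0.40, every version rejected in at least 94% of trials under decay-corrected subtraction. There the fault lies in interval width, not significance.

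Ranking AUCinf ahead of CMAX would be partly a matter of choice, since the SAP lists its endpoints unranked. The repair needs no such ranking.

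**Conclusion.** The point holds as a fault of specification. No model is written for the stated endpoints, and the scale is unresolved; both follow from the text alone. On serial samples with a participant intercept only, the standard error is invalid in a direction the SAP does not fix: about 0 to 0.6 type I error across the assumed inputs, against 0.05. Those figures rest on assumed sample size, sampling and variability. The ln question is smaller: for per-session AUC, logged and unlogged analyses disagreed on significance in 2–6% of simulated trials with no difference and in 0–18% at a true ratio of 0.8. This should be corrected. Confidence is medium, because the sound readings cannot be excluded.

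**What to change.** - Make the primary treatment comparison a linear mixed model with treatment, order and random participant, fitted to one value per participant per session for each stated endpoint.
- Put AUCinf and CMAX on the ln scale, and state how non-positive baseline-adjusted values are handled.
- Say that the repeated measures ANOVA is this same model, or delete it.
- Keep any serial-concentration model as supportive, on a stated scale, with sampling time and a session-within-participant random effect.
- Correct the reversed AUCinf and AUClast definitions.

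The cost is SAP wording and a re-run on existing data. For AUCinf and CMAX the result becomes a geometric mean ratio, so the arithmetic means in the descriptive summary will no longer match it directly. Intervals may widen. Because Primary Analysis is written in the past tense, the model already run should be reported alongside, with the change dated.

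### The endpoints are single-value PK parameters, but the only mixed model and ANOVA specified have serial plasma concentrations as outcome, so the treatment effect they test is in general neither the AUCinf nor the CMAX ratio

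*SAP*

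**What the plan says.** Study Endpoints sets out what is to be compared: "Endpoint (s): Systemic Nicotine Exposure - Baseline Adjusted AUC (Inf), TMAX, CMAX, Half-Life, and PK-Predicted Dose". Each of these yields one number per participant per session. The method is given there only as a label: "Analysis: Linear mixed model".

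Primary Analysis supplies the detail. For the ANOVA: "Following ln-transformation of plasma concentrations treatment effects were compared by means of repeated measures ANOVA". For the mixed model, it says that "a linear mixed model was used to account for non-independence in sequential measurements", and then: "In building the linear mixed-models, baseline-adjusted plasma nicotine concentrations were considered the dependent variable". The covariates are given as follows: "These models included independent variables of treatment and a dichotomized variable defining order of product assignment". Participant is the grouping factor for the random effects. Sampling time is not among the listed terms.

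Elsewhere, AUC and PK-predicted dose appear under descriptive statistics, and Secondary Analysis summarises the PK data descriptively.

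The Abbreviations list defines AUCinf as "Area under the plasma concentration time curve from zero to the last measured time" and AUClast as "Area under the plasma concentration time curve extrapolated from zero".

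**The concern.** The endpoint list and the specified test do not meet. A reader of the endpoints expects an EC/TC comparison of total exposure (AUCinf) and of peak (CMAX). A programmer following Primary Analysis would compare average concentrations across whatever blood samples were drawn.

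These are different quantities. AUC weights each concentration by the time interval it represents, and CMAX uses the highest concentration only. The concentration model weights every sample equally, so a schedule with many early samples gives the absorption phase most of the weight. If EC and TC differ in speed of absorption, the treatment effect moves with the schedule while the true AUCinf ratio stays fixed. The SAP cannot presume that the curves have the same shape, because TMAX and half-life are themselves endpoints.

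At stake is the main conclusion. A ratio from the specified model could be reported as a difference in nicotine exposure when it is not an estimate of any listed endpoint.

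**Working it through.** **What the model estimates.** The SAP gives no figure to reproduce, so start from the model. With complete ln-scale data at K sampling times and treatment and order as the only covariates, the expected treatment effect is

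δ = (1/K) × Σ ln[C_EC(t_k) / C_TC(t_k)].

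Adding sampling time as a further factor leaves this average unchanged on complete data. If C_EC(t) = r × C_TC(t) at every t, then δ = ln r and the AUCinf and CMAX ratios are both r, so nothing is distorted. Otherwise δ depends on the t_k.

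**Inputs, all assumed.** The SAP gives no curves or sampling times; the protocol may.

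- One-compartment curves with first-order absorption, C(t) ∝ [ka/(ka − ke)] × [exp(−ke·t) − exp(−ka·t)], scaled to equal AUCinf, so the true ratio is 1.00.
- Absorption rates, fast/slow: 0.5/0.1, 0.3/0.1 and 0.2/0.05 per min. Half-life 60, 120 or 150 min. Ratios are slow over fast.
- Schedules in min: A8 = 5, 10, 15, 30, 60, 120, 180, 240; A12 = 2, 5, 10, 15, 20, 30, 45, 60, 90, 120, 180, 240; E20 and E30 = every 20 or 30 min to 240.

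**One case in full** (0.5/0.1, half-life 120 min, A8). The ln concentration ratios at the eight times are −0.843, −0.439, −0.230, −0.013, 0.044, 0.048, 0.048 and 0.048. Their sum is −1.337, the mean is −1.337/8 = −0.167, and exp(−0.167) = 0.85. The same two curves have an AUCinf ratio of 1.00 and a CMAX ratio of 0.88.

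**All nine curve pairs:**

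| Schedule | ln concentration model | Untransformed mean ratio | Trapezoidal AUCinf, same samples |
|---|---|---|---|
| A8 | 0.740–0.889 | 0.712–0.853 | 0.989–1.002 |
| A12 | 0.712–0.860 | 0.744–0.862 | 0.999–1.002 |
| E20 | 1.008–1.124 | 0.989–1.057 | 1.017–1.060 |
| E30 | 1.024–1.147 | 1.008–1.079 | 1.024–1.081 |

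The true CMAX ratio is 0.767–0.920. The untransformed column matters because the sentence that fixes the dependent variable does not repeat the ln step. Leaving it out does not remove the distortion on early-dense schedules.

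**Sensitivity to the assumed curves.** With absorption 0.3 against 0.05 per min, half-life 120 min and equal AUCinf, the ln model targets 0.44 on samples at 2–30 min, 0.59 on samples at 2–240 min and 0.84 on a later-weighted set to 360 min. The size therefore depends heavily on what is assumed.

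**Secondary: test level, if the only random effect is a participant intercept.** Simulation with identical curves, 12, 24 or 36 participants, between-participant SD 0.4, residual SD 0.2 (ln scale), nominal level 5%. Rejection by the ln concentration model, by SD of the participant-by-period effect:

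- SD 0: 0%
- SD 0.1: 0.4–2.6%
- SD 0.2: 8–20%
- SD 0.3: 21–37%

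A paired test on session means of the same ln concentrations stays near nominal, at about 4–8%.

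**The case against.** The strongest reply is that the serial-sample reading is uncharitable. The mixed-model label stands directly under the endpoint list. The SAP speaks of models in the plural and says the crossover analysis followed standard procedures. Treatment, order and participant without time is what one value per period would need. CMAX is itself a plasma concentration.

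Part of this stands. A reader might infer that the SAP assigns no inferential method to AUCinf or CMAX at all. That goes too far, because a mixed model is nominally assigned to them. But the only dependent variable ever named is concentrations, the measurements are called sequential, and the ANOVA is also on ln concentrations. A programmer following the text would not fit AUCinf.

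Three further limits stand:

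- **Test level.** A reader might infer that the false-positive rate is inflated. The SAP does not limit the random effects to an intercept. Even under that reading the error can go either way, and it depends on a variance the SAP does not give.
- **The remedy is not free of schedule effects.** On even schedules, sampled AUCinf shares much of the error. With unequal shapes (0.5/0.1, 24 participants) and a true AUCinf ratio of 1.00, the ln AUCinf model rejects in 7–9% of trials on E20 and E30 at participant-by-period SD 0.2. At SD 0–0.1 it rejects in 10–19%, against 0.5–11% for the concentration model.
- **The abbreviation entries.** A reader might infer that the AUC endpoint is undefined. The standard names make the intent reasonably clear. This is a labelling error to correct, not a second analysis flaw.

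**Conclusion.** The point holds: an endpoint list of single-value PK parameters is paired with a specified analysis of serial concentrations, and no sentence makes AUCinf or CMAX the outcome of a test. This rests on the text alone.

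That the treatment effect depends on the schedule follows from the listed terms, given complete data and curves that are not proportional. Its size is illustrative only. With equal AUCinf, the clear contrast is on early-dense schedules, 0.71–0.89 against 0.99–1.00 for sampled AUCinf. On even schedules, 1.01–1.15 against 1.02–1.08, it is small. With proportional curves there is none on the ln scale.

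The documents do not support saying that this trial's result is biased by a known amount or in a known direction. The test-level issue is conditional and secondary. The change is still needed, because it concerns the primary analysis and decides what the reported ratio means.

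**What to change.** In Primary Analysis, change the sentence that fixes the dependent variable. The crossover linear mixed model should be fitted to one value per participant per treatment: ln baseline-adjusted AUCinf, ln CMAX and ln PK-predicted dose. Use treatment, sequence and period as fixed effects and participant as random effect; the single order variable now listed could mean either sequence or period. Report EC/TC geometric mean ratios with 95% CI. Keep the concentration model as a supportive analysis, described as an average over the sampling times. Correct the AUCinf and AUClast entries in the Abbreviations list. Primary Analysis is partly written in the past tense, so label the change post hoc if the data have already been analysed.

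The cost is SAP wording and a re-run on parameters the SAP already calls for; no new data are needed. Intervals may become wider. Under the simulation variances above, the ln AUCinf interval is 0.77–1.10 times the width of the participant-intercept concentration model's interval at participant-by-period SD 0. At SD 0.3 it is 1.77–2.51 times as wide, but there the concentration model's interval is too narrow.

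### The mixed model's two-level 'order' covariate is not defined as sequence or period; if it is sequence, the EC–TC contrast is not adjusted for a shift between the first and second stay

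*SAP*

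**What the plan says.** The Study Design section sets up a two-arm within-subject crossover of EC against TC. Study Endpoints fixes the conditions of the PK day ("On the first hospital day in each treatment arm the subject will use their product at 9 AM in a standardized protocol") and names the method for the PK endpoints ("Analysis: Linear mixed model") without listing model terms.

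The terms appear only at the end of Primary Analysis:

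- Outcome: "baseline-adjusted plasma nicotine concentrations were considered the dependent variable", after ln-transformation.
- Fixed effects: "These models included independent variables of treatment and a dichotomized variable defining order of product assignment".
- Random effects: "Participant IDs were used as group factor to estimate random effects".

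Periods are mentioned once, as the reason for using a mixed model: "To account for the relatedness in the plasma nicotine measures within each subject during the two treatment periods". No period variable is listed as a covariate.

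**The concern.** A two-level 'order' variable in a two-period crossover can mean two things. It can be sequence (EC first or TC first), which takes one value per participant. Or it can be period (first or second stay), which changes within a participant. The words point to sequence but do not settle the matter, so two analysts could fit different models from the same sentence.

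The choice matters because the EC–TC contrast is made within participants. A sequence term explains differences between groups of participants and leaves that contrast untouched. If nicotine levels differ between the first and second stay for reasons unrelated to product, only a period term removes the difference. Without one, the shift biases the estimate when the two sequences are unequal in size, and it enters the error term even when they are equal.

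**Working it through.** The SAP gives no sample size, allocation, SD or expected effect, so there is no stated figure to reproduce. Every numerical input below is an assumption. The design, outcome, fixed effects and random effect come from the SAP, and so does the test level ("All significance tests will be two-sided with an alpha level set at 0.05").

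**Bias with complete data.** Let τ be the true EC–TC difference on the ln scale and δ the first-minus-second-stay shift. The within-participant difference has mean τ + δ in the EC-first group (n₁) and τ − δ in the TC-first group (n₂). Without period, the estimate is the mean over all participants:

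τ + δ(n₁ − n₂)/N

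Generalised least squares with a random participant intercept confirms this. Treatment + sequence gives the same treatment coefficient as treatment alone, while treatment + period, with or without sequence, gives zero bias at every split tried.

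For an assumed N = 24, the error in the EC/TC ratio is exp(δ(n₁ − n₂)/N) − 1:

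| δ (as a ratio) | 12:12 | 13:11 (2/24) | 14:10 (4/24) |
|---|---|---|---|
| 0.1 (11%) | 0 | 0.84% | 1.68% |
| 0.2 (22%) | 0 | 1.68% | 3.39% |
| 0.3 (35%) | 0 | 2.53% | 5.13% |

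**Serial-concentration model.** At 14:10, with 10 samples per stay, δ = 0.2, residual SD 0.5 and τ = 0, 20,000 simulated trials gave a mean estimate of 0.033 without period (0.2 × 4/24 = 0.033) and 0.000 with it. Type I error was about 0.11 without period and 0.05 with it.

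**Dropout.** Start from 12:12 and let 2 or 4 TC-first participants miss their second stay. With an assumed between-participant variance of 0.25 and within-participant variance 0.42²/2 = 0.088, treatment + sequence leaves 0.080 or 0.179 of δ in the estimate. Using completers only, the shares are 2/22 = 0.091 and 4/20 = 0.200.

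**Standard error at 12:12, one value per stay** (for example AUC or CMAX, if the same fixed effects are used there). With SD of differences 0.42, the ratio of the SE without period to the SE with it is

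√(1 + δ² × (24/23)/0.42²)

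- δ = 0.1: 1.029
- δ = 0.2: 1.112
- δ = 0.3: 1.238

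Simulation gave 1.029, 1.112 and 1.239. In a separate run with residual SD 0.3 per stay and a true difference of 0.25, power at δ = 0.2 was 0.72 without period and 0.79 with it; type I error was 0.031 and 0.050.

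**Standard error at 12:12, serial concentrations.** With 10 samples per stay, independent given a participant intercept, the simulated ratio ran from 1.008 (δ = 0.2, residual SD 0.8) to 1.046 (δ = 0.3, residual SD 0.5).

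**Limit of the remedy.** If stays vary within a participant beyond a common shift, a period term does not make the serial model's SE valid. At 12:12 with δ = 0.2 and residual SD 0.5, participant-by-stay SDs of 0.1, 0.2 and 0.3 gave type I errors of 0.09, 0.20 and 0.32 without period and 0.10, 0.21 and 0.33 with it. Analysing per-stay means with period gave 0.05 in all three.

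**The case against.** The strongest reply is that this is a naming query. The model does contain a two-level order covariate, and the section says the crossover analysis followed standard procedures; if the variable was coded per stay, the analysis is already right. That possibility stands and makes the concern conditional. It does not remove it, because sequence is the plainer reading and a general appeal to standard practice names no term.

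Bias also needs three things together: sequence coding, unequal sequences or one-sided dropout, and a real shift. The SAP gives evidence of neither imbalance nor a shift. The fixed clock time, fixed hospital day, standardised EC puffing and baseline adjustment all limit a shift, though they do not exclude one. At N = 24, δ = 0.2 and SD of differences 0.42, the SE is 0.42/√24 = 0.086, so the bias is about 0.19 SE at 13:11 (0.0167/0.086) and 0.39 SE at 14:10 (0.0333/0.086). At equal split the one-value test is conservative, so the cost is power and not false positives.

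The largest SE figures apply to one value per stay, whereas the sentence quoted concerns serial concentrations. There the cost may be below 1% to 5%. The listed terms include no sampling time, so the shape of the concentration curve may stay in the residual. With residual SD 1.0 to 1.5 (assumed), √(1 + δ²/(4 SD²)) gives 1.002 to 1.011 for δ of 0.2 to 0.3. This stands too. So does the point that the random-effects structure can matter more than the period term when stays vary.

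**Conclusion.** The concern holds as a minor one. The SAP writes out its primary model and leaves one of its two fixed effects open; on the plainer reading, that effect does nothing for the contrast of interest. This does not show that the EC–TC estimate is biased. If 'order' is sequence, the sequences are unequal and there is a shift, the ratio is off by low single-digit percentages under the splits and shifts assumed here; 5.1% and the 24% SE increase are upper illustrations, not expected effects. With equal, complete sequences there is no bias and the loss is one of precision, small for the serial model. If 'order' was already coded per stay, only the name needs correcting. Confidence is medium because the coding cannot be read from the document.

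**What to change.** State the fixed effects as treatment and period (first or second stay), with sequence optional and participant random. Do so for the concentration model and for each PK parameter analysed by mixed model. If 'order' was coded per stay, rename it period.

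The cost is one degree of freedom and a word in the model statement; the stay is known for every record. When no shift exists, the loss is negligible at equal split (simulated power 0.793 with or without period) and small at 14:10 (0.788 without, 0.775 with). Whether the random part also needs a participant-by-stay term should be decided and stated separately, since the period term does not settle it.
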